Appendix 2 Schedule of Patient-Reported Outcome Assessments

Visit	Timepoint	Sample Type(s)
Cycles 1 and 2, Day 1	Predose and prior to disease status assessments ^a	
 PROMIS® Item Bank v2.0–Physical Functioning–Short Form 10b [REDACTED] [REDACTED] [REDACTED] [REDACTED] [REDACTED] MIS PGI-S
Cycle 3, Day 1 and every other cycle until treatment discontinuation (i.e., Cycles 5, 7, 9, etc.)	Predose and prior to disease status assessments ^a	
 [REDACTED] MIS PGI-S PGI-CI
Cycle 4, Day 1 and every other cycle until treatment discontinuation (i.e., Cycles 6, 8, 10, etc.)	Predose and prior to disease status assessments ^a	
 PROMIS® Item Bank v2.0–Physical Functioning–Short Form 10b [REDACTED] [REDACTED] [REDACTED] [REDACTED] PGI-S PGI-CI
Treatment discontinuation visit	At visit	
 As indicated based on alternating schedule of assessment per cycle.

MIS=Most Important Symptoms; PGI-CI=Patient Global Impression of Change and its Importance; PGI-S=Patient Global Impression of Severity; PK=pharmacokinetic; PRO=patient-reported outcome; [REDACTED]

PROMIS =Patient-Reported Outcomes Measurement Information System

^a To be completed before the patient receives any information on disease status and prior to the performance of non-PRO assessments and the administration of study treatment. Study personnel should review all questionnaires for completeness before the patient leaves the investigational site. In scenarios where other clinical activities performed ≤ 96 hours before the visit dates (e.g., those specified in [Appendix 1](#) footnote h) are intended for treatment determination, PROs can be completed ≤ 96 hours before the scheduled visit, prior to those clinical activities.

Appendix 4

Response Evaluation Criteria in Solid Tumors, Version 1.1 (RECIST v1.1)

Selected sections from the Response Evaluation Criteria in Solid Tumors, Version 1.1 (RECIST v1.1), (Eisenhauer et al. 2009) are presented below, with slight modifications from the original publication and the addition of explanatory text as needed for clarity.¹

TUMOR MEASURABILITY

At baseline, tumor lesions/lymph nodes will be categorized as measurable or non-measurable as described below. All measurable and non-measurable lesions should be assessed at screening and at subsequent protocol-specified tumor assessment timepoints. Additional assessments may be performed as clinically indicated for suspicion of progression.

DEFINITION OF MEASURABLE LESIONS

Tumor Lesions

Tumor lesions must be accurately measured in at least one dimension (longest diameter in the plane of measurement is to be recorded) with a minimum size as follows:

- 10 mm by computed tomography (CT) or magnetic resonance imaging (MRI) scan (CT/MRI scan slice thickness/interval ≤ 5 mm)
- 10-mm caliper measurement by clinical examination (lesions that cannot be accurately measured with calipers should be recorded as non-measurable)
- 20 mm by chest X-ray

Malignant Lymph Nodes

To be considered pathologically enlarged and measurable, a lymph node must be ≥ 15 mm in the short axis when assessed by CT scan (CT scan slice thickness recommended to be ≤ 5 mm). At baseline and follow-up, only the short axis will be measured and followed. Additional information on lymph node measurement is provided below (see "Identification of Target and Non-Target Lesions" and "Calculation of Sum of Diameters").

¹ For clarity and for consistency within this document, the section numbers and cross-references to other sections within the article have been deleted and minor changes have been made.

DEFINITION OF NON-MEASURABLE LESIONS

Non-measurable tumor lesions encompass small lesions (longest diameter < 10 mm or pathological lymph nodes with short axis \geq 10 mm but < 15 mm) as well as truly non-measurable lesions. Lesions considered truly non-measurable include leptomeningeal disease, ascites, pleural or pericardial effusion, inflammatory breast disease, lymphangitic involvement of skin or lung, peritoneal spread, and abdominal mass/abdominal organomegaly identified by physical examination that is not measurable by reproducible imaging techniques.

SPECIAL CONSIDERATIONS REGARDING LESION MEASURABILITY

Bone lesions, cystic lesions, and lesions previously treated with local therapy require particular comment, as outlined below.

Bone Lesions:

- Technetium-99m bone scans, sodium fluoride positron emission tomography scans, and plain films are not considered adequate imaging techniques for measuring bone lesions. However, these techniques can be used to confirm the presence or disappearance of bone lesions.
- Lytic bone lesions or mixed lytic-blastic lesions with identifiable soft tissue components that can be evaluated by cross-sectional imaging techniques such as CT or MRI can be considered measurable lesions if the soft tissue component meets the definition of measurability described above.
- Blastic bone lesions are non-measurable.

Cystic Lesions:

- Lesions that meet the criteria for radiographically defined simple cysts should not be considered malignant lesions (neither measurable nor non-measurable) since they are, by definition, simple cysts.
- Cystic lesions thought to represent cystic metastases can be considered measurable lesions if they meet the definition of measurability described above. However, if non-cystic lesions are present in the same patient, these are preferred for selection as target lesions.

Lesions with Prior Local Treatment:

- Tumor lesions situated in a previously irradiated area or in an area subjected to other loco-regional therapy are usually not considered measurable unless there has been demonstrated progression in the lesion

METHODS FOR ASSESSING LESIONS

All measurements should be recorded in metric notation, using calipers if clinically assessed. All baseline evaluations should be performed as close as possible to the treatment start and never more than 4 weeks before the beginning of the treatment.

The same method of assessment and the same technique should be used to characterize each identified and reported lesion at baseline and during the study. Imaging-based evaluation should always be the preferred option.

CLINICAL LESIONS

Clinical lesions will only be considered measurable when they are superficial and ≥ 10 mm in diameter as assessed using calipers (e.g., skin nodules). For the case of skin lesions, documentation by color photography, including a ruler to estimate the size of the lesion, is suggested.

CHEST X-RAY

Chest CT is preferred over chest X-ray, particularly when progression is an important endpoint, since CT is more sensitive than X-ray, particularly in identifying new lesions. However, lesions on chest X-ray may be considered measurable if they are clearly defined and surrounded by aerated lung.

CT AND MRI SCANS

CT is the best currently available and reproducible method to measure lesions selected for response assessment. In this guideline, the definition of measurability of lesions on CT scan is based on the assumption that CT slice thickness is ≤ 5 mm. When CT scans have slice thickness of > 5 mm, the minimum size for a measurable lesion should be twice the slice thickness. MRI is also acceptable.

If prior to enrollment it is known that a patient is unable to undergo CT scans with intravenous (IV) contrast because of allergy or renal insufficiency, the decision as to whether a non-contrast CT or MRI (without IV contrast) will be used to evaluate the patient at baseline and during the study should be guided by the tumor type under investigation and the anatomic location of the disease. For patients who develop contraindications to contrast after baseline contrast CT is done, the decision as to whether non-contrast CT or MRI (enhanced or non-enhanced) will be performed should also be based on the tumor type and the anatomic location of the disease, and should be optimized to allow for comparison with the prior studies if possible. Each case should be discussed with the radiologist to determine if substitution of these other approaches is possible and, if not, the patient should be considered not evaluable from that point forward. Care must be taken in measurement of target lesions and interpretation of

non-target disease or new lesions on a different modality, since the same lesion may appear to have a different size using a new modality.

ENDOSCOPY, LAPAROSCOPY, ULTRASOUND, TUMOR MARKERS, CYTOLOGY, HISTOLOGY

Endoscopy, laparoscopy, ultrasound, tumor markers, cytology, and histology cannot be used for objective tumor evaluation.

ASSESSMENT OF TUMOR BURDEN

To assess objective response or future progression, it is necessary to estimate the overall tumor burden at baseline and use this as a comparator for subsequent measurements.

IDENTIFICATION OF TARGET AND NON-TARGET LESIONS

When more than one measurable lesion is present at baseline, all lesions up to a maximum of five lesions total (and a maximum of two lesions per organ) representative of all involved organs should be identified as target lesions and will be recorded and measured at baseline. This means that, for instances in which patients have only one or two organ sites involved, a maximum of two lesions (one site) and four lesions (two sites), respectively, will be recorded. Other lesions (albeit measurable) in those organs will be considered non-target lesions.

Target lesions should be selected on the basis of their size (lesions with the longest diameter) and should be representative of all involved organs, but in addition should lend themselves to reproducible repeated measurements. It may be the case that, on occasion, the largest lesion does not lend itself to reproducible measurement, in which circumstance the next largest lesion that can be measured reproducibly should be selected.

Lymph nodes merit special mention since they are normal anatomical structures that may be visible by imaging even if not involved by tumor. As noted above, pathological nodes that are defined as measurable and may be identified as target lesions must meet the criterion of a short axis of ≥ 15 mm by CT scan. Only the short axis of these nodes will contribute to the baseline sum. The short axis of the node is the diameter normally used by radiologists to judge if a node is involved by solid tumor. Lymph node size is normally reported as two dimensions in the plane in which the image is obtained (for CT, this is almost always the axial plane; for MRI, the plane of acquisition may be axial, sagittal, or coronal). The smaller of these measures is the short axis. For example, an abdominal node that is reported as being 20 mm \times 30 mm has a short axis of 20 mm and qualifies as a malignant, measurable node. In this example, 20 mm should be recorded as the node measurement. All other pathological nodes (those with short axis ≥ 10 mm

but < 15 mm) should be considered non-target lesions. Nodes that have a short axis of < 10 mm are considered non-pathological and should not be recorded or followed.

All lesions (or sites of disease) not selected as target lesions (measurable or non-measurable), including pathological lymph nodes, should be identified as non-target lesions and should also be recorded at baseline. Measurements are not required. It is possible to record multiple non-target lesions involving the same organ as a single item on the Case Report Form (CRF) (e.g., "multiple enlarged pelvic lymph nodes" or "multiple liver metastases").

CALCULATION OF SUM OF DIAMETERS

A sum of the diameters (longest diameter for non-lymph node lesions, short axis for lymph node lesions) will be calculated for all target lesions at baseline and at each subsequent tumor assessment as a measure of tumor burden.

Measuring Lymph Nodes

Lymph nodes identified as target lesions should always have the actual short axis measurement recorded (measured in the same anatomical plane as the baseline examination), even if the node regresses to < 10 mm during the study. Thus, when lymph nodes are included as target lesions, the sum of diameters may not be zero even if complete response criteria are met, since a normal lymph node is defined as having a short axis of < 10 mm.

Measuring Lesions That Become Too Small to Measure

During the study, all target lesions (lymph node and non-lymph node) recorded at baseline should have their actual measurements recorded at each subsequent evaluation, even when very small (e.g., 2 mm). However, sometimes lesions or lymph nodes that are recorded as target lesions at baseline become so faint on CT scan that the radiologist may not feel comfortable assigning an exact measurement and may report them as being too small to measure. When this occurs, it is important that a value be recorded on the CRF, as follows:

- If it is the opinion of the radiologist that the lesion has likely disappeared, the measurement should be recorded as 0 mm.
- If the lesion is believed to be present and is faintly seen but too small to measure, a default value of 5 mm should be assigned and "too small to measure" should be ticked. (Note: It is less likely that this rule will be used for lymph nodes since they usually have a definable size when normal and are frequently surrounded by fat such as in the retroperitoneum; however, if a lymph node is believed to be present and is faintly seen but too small to measure, a default value of 5 mm should be assigned in this circumstance as well and "too small to measure" should also be ticked).

To reiterate, however, if the radiologist is able to provide an actual measurement, that should be recorded, even if it is <5 mm, and in that case "too small to measure" should not be ticked.

Measuring Lesions That Split or Coalesce on Treatment

When non-lymph node lesions fragment, the longest diameters of the fragmented portions should be added together to calculate the sum of diameters. Similarly, as lesions coalesce, a plane between them may be maintained that would aid in obtaining maximal diameter measurements of each individual lesion. If the lesions have truly coalesced such that they are no longer separable, the vector of the longest diameter in this instance should be the maximum longest diameter for the coalesced lesion.

EVALUATION OF NON-TARGET LESIONS

Measurements are not required for non-target lesions, except that malignant lymph node non-target lesions should be monitored for reduction to < 10 mm in short axis.

Non-target lesions should be noted at baseline and should be identified as "present" or "absent" and (in rare cases) may be noted as "indicative of progression" at subsequent evaluations. In addition, if a lymph node lesion shrinks to a non-malignant size (short axis < 10 mm), this should be captured on the CRF as part of the assessment of non-target lesions.

RESPONSE CRITERIA

CRITERIA FOR TARGET LESIONS

Definitions of the criteria used to determine objective tumor response for target lesions are provided below:

- Complete response (CR): Disappearance of all target lesions
Any pathological lymph nodes must have reduction in short axis to < 10 mm.
- Partial response (PR): At least a 30% decrease in the sum of diameters of all target lesions, taking as reference the baseline sum of diameters, in the absence of CR
- Progressive disease (PD): At least a 20% increase in the sum of diameters of target lesions, taking as reference the smallest sum of diameters at prior timepoints (including baseline)
In addition to the relative increase of 20%, the sum of diameters must also demonstrate an absolute increase of ≥ 5 mm.
- Stable disease (SD): Neither sufficient shrinkage to qualify for CR or PR nor sufficient increase to qualify for PD

CRITERIA FOR NON-TARGET LESIONS

Definitions of the criteria used to determine the tumor response for the group of non-target lesions are provided below. While some non-target lesions may actually be measurable, they need not be measured and instead should be assessed only qualitatively at the timepoints specified in the schedule of activities.

- CR: Disappearance of all non-target lesions and (if applicable) normalization of tumor marker level

All lymph nodes must be non-pathological in size (< 10 mm short axis).

- Non-CR/Non-PD: Persistence of one or more non-target lesions and/or (if applicable) maintenance of tumor marker level above the normal limits
- PD: Unequivocal progression of existing non-target lesions

SPECIAL NOTES ON ASSESSMENT OF PROGRESSION OF NON-TARGET LESIONS

Patients with Measurable and Non-Measurable Disease

For patients with both measurable and non-measurable disease to achieve unequivocal progression on the basis of the non-target lesions, there must be an overall level of substantial worsening in non-target lesions in a magnitude that, even in the presence of SD or PR in target lesions, the overall tumor burden has increased sufficiently to merit discontinuation of therapy. A modest increase in the size of one or more non-target lesions is usually not sufficient to qualify for unequivocal progression status. The designation of overall progression solely on the basis of change in non-target lesions in the face of SD or PR in target lesions will therefore be extremely rare.

NEW LESIONS

The appearance of new malignant lesions denotes disease progression; therefore, some comments on detection of new lesions are important. There are no specific criteria for the identification of new radiographic lesions; however, the finding of a new lesion should be unequivocal, that is, not attributable to differences in scanning technique, change in imaging modality, or findings thought to represent something other than tumor (for example, some "new" bone lesions may be simply healing or flare of preexisting lesions). This is particularly important when the patient's baseline lesions show PR or CR. For example, necrosis of a liver lesion may be reported on a CT scan report as a "new" cystic lesion, which it is not.

A lesion identified during the study in an anatomical location that was not scanned at baseline is considered a new lesion and will indicate disease progression.

If a new lesion is equivocal, for example because of its small size, continued therapy and follow-up evaluation will clarify if it represents truly new disease. If repeat scans confirm

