4.3.2.3 Atezolizumab and Tiragolumab/Placebo

The following rules apply as long as neither atezolizumab nor tiragolumab/placebo has been permanently discontinued:

- Treatment cycles will normally begin with dosing of atezolizumab and tiragolumab/placebo on Day 1 of each 21-day cycle. [REDACTED]

- [REDACTED]

Guidelines for treatment interruption or discontinuation are provided in Section [5.1.4.2](#) and [Appendix 16](#).

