Patients will undergo tumor assessments at baseline, every 6 weeks (\pm 7 days) for the first 30 weeks following Day 1 of Cycle 1, and every 9 weeks (\pm 7 days) after completion of the Week 30 tumor assessment. Tumor assessments will continue per schedule regardless of treatment delays until radiographic disease progression per RECIST v1.1 or loss of clinical benefit for patients who continue study treatment after radiographic

disease progression per RECIST v1.1, withdrawal of consent, death, or study termination by the Sponsor, whichever occurs first. At the investigator's discretion, scans must also be performed at any time if progressive disease or loss of clinical benefit is suspected.

Patients who discontinue study treatment (for any reason, including, but not limited to clinical decline or toxicity) in the absence of radiographic disease progression per RECIST v.1.1 will continue to undergo tumor response assessments per the schedule described above, regardless of whether a new anti-cancer therapy is started. Tumor assessments will continue until radiographic disease progression per RECIST v1.1, withdrawal of consent, death, or study termination by the Sponsor, whichever occurs first

Response will be assessed by the investigator on the imaging modalities detailed above, using RECIST v1.1 (see [Appendix 4](#)). The investigator's assessment of overall tumor response at all timepoints should only be based on RECIST v1.1. Assessments should be performed by the same evaluator, if possible, to ensure internal consistency across visits.

Investigator assessment of overall tumor response at all timepoints will be only based on RECIST v1.1. Tumor assessments must be continued after disease progression per RECIST v1.1 for patients who receive study treatment beyond progression. This includes continued measurement of target lesions, evaluation of non-target lesions, and evaluation of any newly identified lesions at all subsequent assessments.

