5.1.4.2 Treatment Interruptions

Study treatment may be temporarily suspended as appropriate for management of toxicity. On the basis of the available characterization of mechanism of action, tiragolumab may cause adverse events similar to but independent of atezolizumab, may exacerbate the frequency or severity of atezolizumab-related adverse events, or may have non-overlapping toxicities with atezolizumab. Because these scenarios may not be distinguished from one another in the clinical setting, immune-mediated adverse events should generally be attributed to both study drugs, and dose interruptions or treatment discontinuation in response to immune-mediated adverse events should be applied to both atezolizumab and tiragolumab/placebo.

[REDACTED]

[REDACTED]

[REDACTED]

[REDACTED]

Dose interruptions may be allowed for reason(s) other than toxicity, such as surgical procedures. The acceptable length of treatment interruption must be based on the investigator's benefit–risk assessment and in alignment with the protocol requirements for the duration of treatment and documented by the investigator. The Medical Monitor is available to advise as needed.

After both study treatments have been discontinued, the patient will be monitored for safety and efficacy as defined in Section 4.6.1.

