6.4.2.4 Patient-Reported Outcomes

TTCD for physical functioning using the PROMIS® Item Bank v2.0–Physical Functioning–Short Form 10b is defined as the time from the date of randomization until the first confirmed clinically meaningful deterioration. Confirmed clinically meaningful deterioration in physical function is defined as a clinically meaningful decrease from baseline that must be held for at least two consecutive assessments, or an initial clinically meaningful decrease from baseline followed by death. A T-score change >4 points is considered to be clinically meaningful for the physical functioning subscale score (Yost et al. 2011).

TTCD will be assessed in all randomized patients who received at least one dose of study treatment. Patients will be grouped based on actual treatment received. Patients who have not experienced a confirmed clinically meaningful deterioration at the clinical cutoff date will be censored at the last time when they completed an assessment. If no baseline or post-baseline assessment is performed, patients will be censored at the randomization date. TTCD [REDACTED] will be analyzed using the same methods as for PFS.

[REDACTED]

[REDACTED]

[REDACTED]

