Appendix 1: Schedule of Activities

Assessment/Procedures	Screening ^a	Treatment	Post-Treatment Follow-Up	
	Days –28 to –1	Day 1 (every 21 Days) (± 3 days for Cycle ≥ 2)	Treatment Discontinuation ^b ≤ [REDACTED] Days after Final Dose	Follow-Up
Chemistry ^k	x ^u	x ^h	x	
Pregnancy test (for women of childbearing potential only)	x ^l	x ^l	x ^l	
Coagulation (INR and aPTT)	x ^u		x	
TSH, free T3 (or total T3), free T4 ^m	x	x ^m	x	
[REDACTED] ⁿ	x			
[REDACTED] ^o	x ^{n, o}	x ^o	x ^o	
Urinalysis ^p	x	As clinically indicated		
Concomitant medications ^q	x ^q	x	x	
Tumor response assessment ^{r, s}	x ^r	x ^s		
Adverse events ^t	x ^t	x ^t	x ^t	x ^t
PROs ^v		Refer to Appendix 2 .		
Atezolizumab IV infusion ^x		x		
Tiragolumab/placebo IV infusion ^x		x		
Serum sample for autoantibody sample (central laboratory) ^y		x ^y		
Serum sample for C-reactive protein (central laboratory) ^y		x ^y		
[REDACTED]				

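### PROMIS physical function follows dosing cycles with no calendar anchor, so if cycles pause during a toxicity hold no score is scheduled until restart, and time to confirmed deterioration may look somewhat too favourable in each arm

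*Combined protocol and SAP*

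**What the plan says.** Appendix 2 gives the PROMIS physical function form predose on Day 1 of Cycles 1 and 2, then at "Cycle 4, Day 1 and every other cycle until treatment discontinuation (i.e., Cycles 6, 8, 10, etc". At the treatment discontinuation visit, PRO forms are completed "As indicated based on alternating schedule of assessment per cycle", so this form is not always due there.

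Appendix 1 sets the nominal treatment visits as "Day 1 (every 21 Days) (± 3 days for Cycle ≥ 2" days. Section 4.3.2.3 says "Treatment cycles will normally begin with dosing of atezolizumab and tiragolumab/placebo on Day 1 of each 21-day cycle"; the text that follows is partly redacted. Section 5.1.4.2 says "Study treatment may be temporarily suspended as appropriate for management of toxicity" and that, for immune-mediated events, "dose interruptions or treatment discontinuation in response to immune-mediated adverse events should be applied to both atezolizumab and tiragolumab/placebo". The finer interruption rules there are redacted too.

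For imaging, Section 4.5.6 states "Tumor assessments will continue per schedule regardless of treatment delays". No comparable wording is visible for PRO forms.

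Time to confirmed deterioration (TTCD) in physical function is a secondary efficacy endpoint (Section 2.1.2). Section 6.4.2.4 requires a T-score decrease of more than 4 points that "must be held for at least two consecutive assessments", or one such decrease followed by death. Patients without an event are censored at their last completed assessment. No time limit between the two assessments is visible.

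**The concern.** The form is attached to days on which a patient is due to be dosed. Section 4.5 allows dosing only when the clinical assessment and local laboratory values are acceptable. A period of toxicity that stops dosing could therefore also stop measurement of physical function, at the time function is most likely to be impaired.

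TTCD needs two low scores in succession, so one absent form can decide whether an event counts. Section 3.4.9 justifies PRO collection partly because clinicians may under-report symptomatic toxicity; a schedule that falls silent during toxicity works against that aim. What is at stake is each arm's own Kaplan-Meier estimate of TTCD, which could show deterioration as rarer or later than it was.

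**Working it through.** The documents state no event count, power or expected value for TTCD, so there is no figure to reproduce. The check uses dates and the confirmation rule. It assumes that cycles pause during a hold and that an event is dated at the first of its two low scores.

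**1. Dates without a hold.** Cycle c starts on day 21(c − 1) + 1. Cycles 1, 2, 4, 6, 8 fall on Days 1, 22, 64, 106, 148, which are Weeks 0, 3, 9, 15, 21. After Cycle 2 the interval is 2 × 3 = 6 weeks.

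**2. Dates with a hold of L weeks.** If the hold falls between two scheduled forms, the interval is 6 + L weeks. The maximum hold is redacted, so L = 3 to 12 is an assumed range.

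| Hold L (weeks) | Interval by cycle, 6 + L | Interval on a calendar schedule | Calendar forms falling inside the gap |
|---|---|---|---|
| 3 | 9 | 6 | 1 |
| 6 | 12 | 6 | 1 |
| 9 | 15 | 6 | 2 |
| 12 | 18 | 6 | 2 |

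For a hold before Cycle 2, the 3-week interval becomes 3 + L = 6, 9, 12 or 15 weeks. If dosing is withheld at an even-cycle visit after the form was completed, and the form is repeated at restart, the gap is only L weeks. The visible text does not say whether it would be repeated.

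**3. Three consequences.**
- *Decline confined to the hold.* By cycle, no form is due, so it is not seen. On a 6-weekly calendar schedule, a decline of D weeks with random phase contains two successive forms with probability (D − 6)/6 for 6 < D < 12, and 1 for D ≥ 12: at D = 9, 3/6 = 50%; at D = 12, 100%. At D ≤ 6 it would not count under either schedule. In TTCD terms this route therefore matters only for holds longer than 6 weeks.
- *Low score before the hold, recovery before restart.* Take a low score at Week 9 (Cycle 4), then a 6-week hold starting at the Cycle 5 visit. Cycle 6 moves from Week 15 to Week 21. If function is still low at Week 15 but recovered by Week 21, the calendar schedule confirms the event and the cycle schedule does not. A 3-week hold is enough for this.
- *Lasting decline.* In the same example, an onset at Week 12 is dated Week 15 by calendar and Week 21 by cycle, 6 weeks late. It is delayed, not lost. With a 3-week hold the grid shifts, and an onset late in the gap can be dated slightly earlier.

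**4. Hold that ends in discontinuation.** If the last form was a low score at an even cycle and the discontinuation visit takes an odd-cycle slot, no form is due. The decline stays unconfirmed unless death follows, and the patient is otherwise censored at the pre-hold form.

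**5. Illustrative simulation of lasting decline.** Assumptions: 40,000 patients per arm, the same true process in both arms, median time to deterioration 26 weeks, median treatment 18 weeks, and one hold of 3, 6 or 12 weeks in 20% of one arm and 20% to 50% of the other. Confirmed events differed between arms by at most about 2 percentage points (largest 32.7% against 30.7%). The 26-week Kaplan-Meier estimates differed by about 2 points at most, in either direction (0.609 against 0.630; 0.666 against 0.651). Medians differed by up to 6 weeks because the curves step only at assessment dates. Holds were assigned independently of decline, so this does not test transient, toxicity-driven declines.

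**The case against.** **Redaction.** The text after the cycle rule in Section 4.3.2.3 and blocks in Section 5.1.4.2 are blacked out, and cycles are said only normally to start with dosing. The plan may already deal with visits during a hold. This stands: the point is conditional, and the sponsor can settle it by reading its own unredacted text.

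**Forms come first.** Appendix 2, footnote a, and Section 4.5.9.1 put PRO forms before other assessments, and up to 96 hours ahead where those decide treatment. A patient held at an even-cycle visit should already have completed the form. This also stands. It moves the start of the silent period to that visit but adds nothing between it and restart.

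**The confirmation rule excludes short dips by design.** True, and step 3 reflects it. It does not cover longer declines, or low scores before a hold whose confirming form was never scheduled.

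**Arm difference.** A reader might infer that the gap flatters the tiragolumab arm, because immune-mediated events in the NSCLC study GO40290 were 65.7% against 47.1% (44/67 and 32/68; difference 18.6 points, 95% CI 2.2 to 35.0). Section 1.6.2.2 attributes that excess mainly to rash and infusion-related reactions, and Section 1.8.2 calls the events generally mild and transient. Grade 3–5 events (41.8% against 44.1%), serious events (34.3% against 35.3%) and withdrawals for adverse events (7.5% against 10.3%) were similar. No interruption rates are given. The documents do not support a differential bias, nor any count of lost events by arm.

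**Descriptive endpoint.** The visible analysis estimates TTCD per arm, with no between-arm test. That limits the consequence, but each arm's estimate is still exposed.

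**Conclusion.** The point holds conditionally. On the visible text, PROMIS physical function has no calendar anchor and no provision for a hold, unlike the scans. If cycles pause, declines during a hold can be missed, left unconfirmed or dated late, and TTCD in each arm may be somewhat too favourable.

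The only size that can be given is the interval: 6 weeks stretching to 9 to 18 weeks for assumed holds of 3 to 12 weeks. The effect on TTCD cannot be derived without the frequency and length of interruptions. Lasting declines are mostly detected late rather than lost. A difference between arms is plausible but not shown. This is an inexpensive improvement to a secondary endpoint; it does not affect the primary endpoint.

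**What to change.** First check the unredacted text of Sections 4.3.2.3 and 5.1.4.2 for how visits and cycle numbers run during a hold. Unless it already provides for PRO forms, amend Appendix 2 as follows:

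- Schedule PROMIS physical function at Weeks 0, 3, 9, 15 and every 6 weeks from Cycle 1 Day 1, with stated windows, whatever happens to dosing, until treatment discontinuation. Without a hold these are the same dates as now.
- During a hold, complete the form at the nearest attended safety, laboratory or scan visit, always before disease-status information and other assessments.
- Always collect it at the treatment discontinuation visit, whichever slot the alternating schedule has reached.

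Reporting form completion and time on hold by arm would also let readers judge any remaining gap.

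**Cost.** An amendment of Appendix 2 with a window table, a few extra paper forms, and visits no longer labelled by cycle. Windows must be wider during holds: scans fall at Weeks 6, 12, 18, 24 and 30, each 3 weeks from a PROMIS date, so ±7 days on both sides does not bridge them. After Week 30 scans are 9-weekly (39, 48, 57, 66, 75), and only every second one (39, 57, 75) coincides. Scan visits alone will therefore not carry the schedule, which is why any attended visit should be allowed.
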